9.1 Steady-state assessment

PKCS dataset will be used for steady-state assessment.

By considering the three day's morning pre-dose concentrations in a given period, steady state analysis will be performed for each subject in each period by using the linear regression analysis to obtain the p-values. The above analyses will be done using procedure PROC REG in SAS, version 9.4 or higher.

For achieving the steady state following procedure should be assessed:

Step 1: For each subject in each period the P-values should be statistically insignificant at 5% level of significance.

If, P-values are found statistically insignificant, those patients are considered to achieve steady state. If, P-values are found significant for particular subject then go for the second step. Go for second step for patients who have missing pre-dose sample for Day 6 or Day 14.

Step 2: Ratio of the pre-dose concentrations of last two pre-dose should be \geq 80% or should be \leq 120.00%.

In case ratio of last two pre-dose concentrations is found to be $\ge 80\%$ or $\le 120.00\%$ patients will be considered to achieve steady state. If two pre-dose concentrations is found to be less than 80% or greater than 120%, patients will not be considered to achieve steady state and will be removed from bioequivalence evaluation.

9.2 BE assessment

PKPS dataset will be used for BE assessment.

9.2.1 Steps of a two stage design according to Potvin C

Page 20 of 30

Stage 1:

Step1:

Evaluate the power at stage 1 using the variance estimate from stage 1, GMR of 0.95 and an α level of 0.05 for each of C_{maxSS} and AUC_{(0- τ)SS} parameters.

Before proceeding to Step 2, notify the sponsor (via email) regarding stage 1 power and CV values. However, the other BE assessment results (e.g. GMR point estimates or confidence intervals) should not be calculated at Step 1 nor shared with the sponsor. After a confirmatory email is received from the sponsor, proceed to Step 2.

Step 2:

Step 2.1: If power (calculated using the observed variability and GMR of 0.95) is greater than or equal to 80% for both of the parameters (C_{maxSS} and $AUC_{(0-\tau)SS}$), evaluate BE at stage 1 using an α level of 0.05 and stop regardless of whether BE is met or not.

OR

Step 2.2: If the power for either of the two parameters (C_{maxSS} or AUC_{(0- τ)SS}) is less than 80%, evaluate BE using an α level of 0.0294.

Step 2.2.1: If the BE criterion is met, stop.

OR

Step 2.2.2: If the BE criterion is not met, calculate the sample size for stage 2 based on the variance estimated at stage 1, GMR of 0.95 and an α level of 0.0294, round up to nearest even number, add 20% subjects for dropouts and continue to stage 2. If the calculated sample size for stage 2 is less than 12, include at least 12 subjects in stage 2. If the GMR point estimate for any parameter (C_{maxSS} or AUC_{(0-\tau)SS}) is outside 80.00%-125.00% then study will not proceed for stage 2.

Stage 2

Evaluate BE at stage 2 using data pooled from both stages and an α level of 0.0294. Stop here whether BE is met or not and regardless of the power achieved.

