### 15.2 Statistical Analysis

SAS® Software, Version 9.4 or higher will be used for statistical analysis of pharmacokinetic parameters CmaxSS and AUC(0-t)ss.

By considering the three day's morning pre-dose concentrations in a given period, steady state analysis will be performed for each subject in each period by using the linear regression analysis to obtain the p-values. The above analyses will be done using procedure PROC REG in SAS, version 9.4 or higher.

For achieving the steady state following procedure should be assessed:

[figure not shown]
Step 1: For each subject in each period the P-values should be statistically insignificant at 5% level of significance.

If, P-values are found statistically insignificant, those patients are considered to achieve steady state. If, P-values are found significant for particular subject then go for the second step. Go for second step for patients who have missing pre-dose sample for Day 6 or Day 14.

Step 2: Ratio of the pre-dose concentrations of last two pre-dose should be  $\geq 80\%$  or should be  $\leq 120.00\%$ .

In case ratio of last two pre-dose concentrations is found to be  $\geq 80\%$  or  $\leq 120.00\%$  patients will be considered to achieve steady state. If two pre-dose concentrations is found to be less than 80% or greater than 120%, patients will not be considered to achieve steady state and will be removed from bioequivalence evaluation.

Two stage design according to Potvin C: Evaluate the power at stage 1 using the variance estimate from stage 1 and an  $\alpha$  level of 0.05. If the power is greater than or equal to 80% (calculated by observed variability and GMR=0.95), evaluate BE at stage 1 using an  $\alpha$  level of 0.05 and stop whether BE is met or not. If the power is less than 80%, evaluate BE using an  $\alpha$  of 0.0294. If the BE criterion is met, stop. If the BE criterion is not met, calculate the sample size based on the variance estimated at stage 1, GMR=0.95 and an  $\alpha$  level of 0.0294 and continue to stage 2. If the ratio is outside 80.00%-125.00% then study will not proceed for stage 2. Evaluate BE at stage 2 using data from both stages and an  $\alpha$  level of 0.0294. Stop here whether BE is met or not and regardless of the power achieved.

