9.2.2 Analysis of Variance

For Stage 1:

The ln-transformed pharmacokinetic parameters (C_{maxSS} and $AUC_{(0-\tau)SS}$) will be analyzed using an ANOVA model with Center, Treatment, Period (Center), Sequence, Sequence*Center as fixed effects and Patient (Within Sequence*Center) as a random effect.

Sequence and Center main effects and Sequence*Center interaction effect will be tested using Patient (within Sequence*Center) mean square from the ANOVA model as the error term. All other main

effects will be tested against residual error (mean square error) from the ANOVA model as the error term.

Main effects will be tested at the 0.05 level of significance, whereas the interaction effect will be tested at the 0.10 level of significance.

Results from each analysis of variance will include formulation least-squares means, the difference between the adjusted formulation means, the standard error associated with the difference and the associated confidence interval. The above analyses will be done using procedure PROC MIXED in SAS, version 9.4 or higher. Kenwart-Roger method for the denominator degrees of freedom will be applied.

For combined Stage 1 and Stage 2 data:

The selection of final statistical model after stage 2 will be based on the centers selected for stage 2:

- If all stage 1 centers will be used in stage 2, then the In-transformed pharmacokinetic parameters (C_{maxSS} and AUC_{(0-r)SS}) will be analyzed using an ANOVA model with the effects of Center, Stage, Treatment, Period (Center*Stage), Sequence, Sequence*Center, Center*Stage, Sequence*Center*Stage as fixed, and Patient (Within Sequence*Center*Stage) as a random effect.
- Alternatively, if all stage 1 centers will not be used in stage 2, then the ln-transformed pharmacokinetic parameters (C_{maxSS} and AUC₍₀₋₇)ss) will be analyzed using an ANOVA model with the effects of Center, Stage, Treatment, Period (Center), Sequence, Sequence*Center as fixed, and Patient (Within Sequence*Center*Stage) as a random effect.

The Sequence, Stage, Center and all included interaction effects will be tested using the Patient (within Sequence*Center*Stage) effect as the error term. All other main effects will be tested against the residual error (mean square error) from the ANOVA model, as the error term.

Main effects will be tested at the 0.05 level of significance, whereas the interaction effects will be tested at the 0.10 level of significance.

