9.2.3 Intra-Subject Variability

Intra-subject variability will be calculated using mean square error of ANOVA for ln-transformed analysis of C_{maxss} and AUC_{(0-τ)ss} for Olaparib.

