4 STATISTICAL METHODOLOGY

Since 2008, a number of adaptive two-stage sequential designs for bioequivalence twosequence, two-period, two-treatment crossover studies have been suggested and evaluated with respect to TIE rate and power (Potvin et al. [1], Montague et al. [2], Karalis et al. [3], Kieser et al. [4], Schuetz [5], Maurer et al. [6], Fuglsang [7], [8], etc.).

The Potvin Method C, introduced by Potvin et al. [1] (although criticized [4], with several adaptations/ alternatives having been suggested) still appears to be the method of choice.

For the current study we developed a modification to the original Potvin Method C, which is described in detail below, and the evaluation of the FDF modified method with regard to the Type I Error (TIE) rate and power is presented in the Results Section below.

The validity of simulation results regarding estimates of the TIE rate and Power depends primarily on the match between the actual/ planned BE evaluation procedure and the procedure for the simulation and evaluation of studies used in estimating TIE and Power.

In the case of a two-stage design, this means that every step in the actual evaluation procedure must be adequately reflected in the program for simulating studies and estimating the TIE rate and power.

For the planned BE study it was decided to apply a two-stage Potvin Method C, but with the following three modifications (see Figure 1 below):

- 1. To include the futility criterion of Point Estimate (PE) at stage 1 (i.e., to stop the study if PE falls outside the range of 0.80-1.25),
- To include the futility criterion of the maximal total sample size, i.e., to stop the study if the total required sample size is greater than the pre-specified maximum (e.g., either 120, 150 or 200), and
- To adjust/decrease the error degrees of freedom (df) for the number of sites in the BE evaluation at the first and final stage of the two stage procedure (i.e., in the estimation of the Type I Error (TIE) rate and power, using simulation).

A Potvin method C design that includes the above three modifications will in this report be referred to as the "FDF modified Potvin Method C design".

[figure not shown]

Figure 1. Potvin Method C (left) and FDF modified Potvin Method C (right) Design Schema

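### The Stage 1 power check and Stage 2 sizing are not tied to the standard error of the within-centre BE model; if they follow the annex, the 80% threshold and the stated 86% power are overstated.

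*SAP*

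**What the plan says.** - **Power check.** SAP 9.2.1, Step 1: "Evaluate the power at stage 1 using the variance estimate from stage 1, GMR of 0.95 and an α level of 0.05", separately for CmaxSS and AUC(0-τ)SS. Protocol 15.2 describes the same power as "calculated by observed variability and GMR=0.95". Neither text gives the sample size, degrees of freedom or SE that enter the formula.
- **Closing rule.** If power, "calculated using the observed variability and GMR of 0.95", is at least 80% for both parameters, Step 2.1 says to "evaluate BE at stage 1 using an α level of 0.05 and stop regardless of whether BE is met or not".
- **Stage 2 sizing.** If Stage 1 power is below 80% and BE is not met at alpha 0.0294, Step 2.2.2 says to "calculate the sample size for stage 2 based on the variance estimated at stage 1, GMR of 0.95" and alpha 0.0294. The result is rounded up to an even number and 20% is added for dropouts, with a minimum of 12.
- **Variability.** SAP 9.2.3: "Intra-subject variability will be calculated using mean square error of ANOVA".
- **BE model.** SAP 9.2.2, Stage 1: "ANOVA model with Center, Treatment, Period (Center), Sequence, Sequence*Center as fixed effects", with patient as a random effect. Centres are pooled until each has at least five evaluable patients and at least one from each sequence.
- **Annexed simulation.** Of its three changes to Potvin C, the one for multiple sites is "To adjust/decrease the error degrees of freedom (df) for the number of sites in the BE evaluation". It states 86% overall power for 56 Stage 1 patients at CV 35%, and SAP 3.1 and Protocol 7.1 repeat that figure.

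**The concern.** The check and the BE test should describe the same analysis. With a separate period effect in each combined centre, test minus reference (T−R) is estimated purely within centres. Its precision depends on the sequence split inside each centre, not only on the MSE and total n. A five-patient centre cannot be 1:1, and the pooling rule allows 4:1. A power figure built on the MSE and total n alone is therefore too high for the model that is fitted.

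Closing is irreversible. A trial whose check reads 80% when its analysis has less loses Stage 2, the safeguard the two-stage design was chosen to provide. Stage 2 sizing has the same gap.

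**Working it through.** **Inputs.** From the documents: n = 56 evaluable, CV 35%, ratio 0.95, limits 80.00–125.00%, Stage 1 alpha 0.05 (SAP 3.1 and 9.2.1); about 20 sites, average and minimum centre size 5, maximum total 120, point-estimate futility range 0.80–1.25 (annex). The annex's error-df formula is n − 2 − (k − 1) for k centres. With 56/5, about 11 centres, this gives 56 − 2 − 10 = 44. Assumed, because the documents do not give them: equal-sized sites, about 20% random loss (70 randomised, 56 evaluable), and the blocking scheme.

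**1. The plan's own figures.** Exact TOST power with SE = sqrt(2·MSE/n), n = 56 and CV 35% is 83.5% when the log-scale SD is sqrt(ln(1 + CV²)), and 81.4% when it is 0.35. The stated minimum of 81% holds either way. Simulating the annex design with this SE and df 44 gives:

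| n1 = 56, CV 35% | Simulated | Annex |
|---|---|---|
| Stage 1 power | 80.2% | 80.4% |
| Proceeding to Stage 2 | 9.9% | 9.8% |
| Final power | 86.1% | 86.0% |
| Type I error | 0.0481 | 0.0483 |

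The annex is therefore reproduced with no term for sequence imbalance within centres.

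**2. SE of the SAP model.** For patients with both periods,

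Var(T−R) = 2·MSE / Σ(4·nTR·nRT/n_c), summed over combined centres.

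The sum equals n only if every centre is 1:1. A 3:2 centre contributes 4·3·2/5 = 4.8 of 5 patients (96%). A 4:1 centre contributes 4·4·1/5 = 3.2 of 5 (64%). Define the information share as this sum divided by n.

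**3. Likely share.** Simulated allocation over 20 equal sites, followed by the SAP pooling rule, gives about 94% with blocks of 4 within site and 87% with one blocked list per stage.

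**4. Effect on the check (n = 56, df 44).** With the annex SE, computed power reaches 80% at an observed CV of 36.7%, so Stage 1 closes at or below that value.

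| Information share | Power at CV 35% | Power at CV 36.7% | Largest CV with real 80% power |
|---|---|---|---|
| 100% (all centres 1:1) | 83.3% | 80.0% | 36.7% |
| 96% (all centres 3:2) | 81.9% | 78.4% | 35.9% |
| 94% (blocks within site) | 81.1% | 77.5% | 35.5% |
| 87% (one list per stage) | 78.0% | 74.2% | 34.1% |

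The affected band of observed CV is about 35.5–36.7% with site blocks and 34.1–36.7% with a list per stage. The df correction alone is negligible (83.5% to 83.3%).

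**5. Overall power at CV 35%, rules as written.** With site blocks it is 83.9% (94% share) to 84.4% (variance inflation 1.05). With a list per stage it is 81.1% (87% share) to 81.2% (inflation 1.15). The annex states 86.0%. Type I error remains 0.048 even at inflation 1.25.

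**6. Stage 2 sizing.** At an observed CV of 40% and alpha 0.0294, the annex SE gives a total of 80. Allowing for inflation of 1.05 or 1.15 gives 84 or 90. Power at 80 patients is 78.8% or 74.7%.

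That step assumes Stage 2 patients are as informative as Stage 1 patients. If all Stage 1 centres are reused, the final model has period effects within centre-by-stage, and SAP 9.2.2 sets no minimum for Stage 2 cells. Many cells would then hold one sequence only and contribute nothing. Simulated Stage 2 information is roughly 43–53% of n at 12 patients and 58–72% at 20, depending on blocking.

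**The case against.** - **The SE form is not written.** A reader might infer that the SAP prescribes the plain 2×2 formula. It does not. That form is inferred from reproducing the annex, whose R code is not shown. What stands is that the formula is unspecified and the only worked example omits the imbalance.
- **Closing in the band is not failing.** A reader might count every such trial as lost. In simulation at CV 35%, 25% of trials (list per stage) or 12% (site blocks) close with model-based power below 80%, but 77% or 79% of these meet BE at alpha 0.05. Trials both closed and failed are about 6% or 2.5% of all. At CV 30% they are 1.7% or 0.5%.
- **The smaller case fits the text at least as well.** Randomisation numbers are built from site ID and order of dosing at that site, which suits site-level lists. Stratification by site is nevertheless not stated.
- **One parameter was simulated.** Step 2.1 requires 80% for both, so the one-parameter closing rates are upper bounds.
- **CV 35% is the plan's maximum expected value.** Losses above it lie outside the planning range, although the annex evaluates power up to 40%.
- **Type I error.** A reader might suspect inflation. None was found.

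These objections limit the size of the problem. They do not restore the 86%, because the within-centre SE can never be smaller than the one that reproduces it.

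**Conclusion.** The concern holds as a power and specification problem. The decision rule does not name its SE. If it follows the annex, trials with an observed CV just below 36.7% close at a nominal 80% when the fitted model has about 78% (site blocks) or 74% (list per stage). At CV 35%, overall power is about 84% or 81% rather than 86%.

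These sizes rest on equal site sizes, about 20% loss, one parameter and equal information per patient in both stages. The last assumption is favourable if all Stage 1 centres are reused. A reader might infer that the trial is underpowered at its planning CV. The documents do not support that, since overall power stays above 80% in both blocking cases. The shortfall is against the stated 86%, and in the purpose of the 80% gate.

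**What to change.** 1. **Step 1.** Compute TOST power from the fitted Stage 1 model: its SE of T−R and Kenward-Roger df, with GMR 0.95 and alpha 0.05. This is the same as replacing n by 2·MSE/SE². The SE does not reveal the point estimate, so Step 1's restriction on calculating the GMR is respected.
2. **Step 2.2.2.** Size Stage 2 from the expected SE of whichever final model in SAP 9.2.2 will be used, at alpha 0.0294. Do not carry over the Stage 1 ratio of effective to actual n, because centre-by-stage period effects with small Stage 2 cells lose much more information.
3. **SAP 3.2.** State whether randomisation is blocked within site.
4. **Annex.** Rerun with the within-centre SE in both stages, confirm type I error, and restate the 86% wherever it appears.

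The cost is a few sentences in the SAP and one rerun. Stage 2 opens somewhat more often. At CV 35% the mean total rises by about 1 patient with site blocks, and by about 3 with a list per stage (58.8 to 61.5 in simulation, with power rising from 81.2% to 84.1%). These gains assume equal information per patient in both stages, so the rerun must confirm them.

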9.2.2 Analysis of Variance

For Stage 1:

The ln-transformed pharmacokinetic parameters (C_{maxSS} and $AUC_{(0-\tau)SS}$) will be analyzed using an ANOVA model with Center, Treatment, Period (Center), Sequence, Sequence*Center as fixed effects and Patient (Within Sequence*Center) as a random effect.

Sequence and Center main effects and Sequence*Center interaction effect will be tested using Patient (within Sequence*Center) mean square from the ANOVA model as the error term. All other main

effects will be tested against residual error (mean square error) from the ANOVA model as the error term.

Main effects will be tested at the 0.05 level of significance, whereas the interaction effect will be tested at the 0.10 level of significance.

Results from each analysis of variance will include formulation least-squares means, the difference between the adjusted formulation means, the standard error associated with the difference and the associated confidence interval. The above analyses will be done using procedure PROC MIXED in SAS, version 9.4 or higher. Kenwart-Roger method for the denominator degrees of freedom will be applied.

For combined Stage 1 and Stage 2 data:

The selection of final statistical model after stage 2 will be based on the centers selected for stage 2:

- If all stage 1 centers will be used in stage 2, then the In-transformed pharmacokinetic parameters (C_{maxSS} and AUC_{(0-r)SS}) will be analyzed using an ANOVA model with the effects of Center, Stage, Treatment, Period (Center*Stage), Sequence, Sequence*Center, Center*Stage, Sequence*Center*Stage as fixed, and Patient (Within Sequence*Center*Stage) as a random effect.
- Alternatively, if all stage 1 centers will not be used in stage 2, then the ln-transformed pharmacokinetic parameters (C_{maxSS} and AUC₍₀₋₇)ss) will be analyzed using an ANOVA model with the effects of Center, Stage, Treatment, Period (Center), Sequence, Sequence*Center as fixed, and Patient (Within Sequence*Center*Stage) as a random effect.

The Sequence, Stage, Center and all included interaction effects will be tested using the Patient (within Sequence*Center*Stage) effect as the error term. All other main effects will be tested against the residual error (mean square error) from the ANOVA model, as the error term.

Main effects will be tested at the 0.05 level of significance, whereas the interaction effects will be tested at the 0.10 level of significance.

If Center*Stage effect is included in the model and is found to be significant, visual exploration of data will be performed to explain the potential reasons for this interaction.

Results from each analysis of variance will include formulation least-squares means, the difference between the adjusted formulation means, the standard error associated with the difference and the associated confidence interval. The above analyses will be done using procedure PROC MIXED in SAS, version 9.4 or higher. Kenwart-Roger method for the denominator degrees of freedom will be applied.

Page 22 of 30

Note: Prior to Stage 1 ANOVA analyses and the assessment of center effect, combining of the small centers will be performed so as to assure that in each of the new, combined centers there will be a minimum of five evaluable patients and that each combined center includes at least one evaluable subject from each of the two sequences.

The small centers will be combined using the following three step procedure:

1. Centers will be first arranged in ascending order based on the number of evaluable patients per center (i.e., from smallest to largest center) and then in ascending order of site label (e.g. A to Z).

2. Starting with the smallest center, a center with less than five evaluable patients will be combined with a subsequent center. If there will be more than one center with less than five patients all these centers will be combined until at least five evaluable subjects will be available in the new, combined center. The procedure will continue with the next center in the arranged order, until all combined centers include at least five evaluable subjects.

3. Starting with the first combined center, a combined center with all subjects from either TR or RT sequence will be joined with the subsequent center until all combined centers include at least one evaluable subject from each of the two sequences.

The combined centers (instead of the original centers) will be used in both stage 1 and stage 2 analyses.

Note: Analysis of study will be performed as per latest/updated Statistical Analysis Plan (SAP).

9.2.3 Intra-Subject Variability

Intra-subject variability will be calculated using mean square error of ANOVA for ln-transformed analysis of C_{maxss} and AUC_{(0-τ)ss} for Olaparib.

